# 1 Clinical Trial Synopsis

Clinical trial title	PICTURE – PT SD aft E r IC U S UR vival				
	Caring for Patients with Traumatic Stress Sequelae following Intensive Medical Care:				
	A multi-center, observer-blinded, randomized, controlled trial with a psychological intervention				
Trial short title	PICTURE				
Trial Registry – nat.	DRKS-ID (German Clinical Trials Register): DRKS00012589				
international	ClinicalTrials.gov: NCT03315390				
Medical Conditions	Post-traumatic stress disorder (PTSD) (ICD-10 F43.1; DSM-5 1.2.7)				
	Post Intensive Care Syndrome (PICS) (Needham et al., 2012)				
Interventions	Experimental intervention:				
	A primary care version of a "Narrative Exposure Therapy" ( NET -oriented, 3 sessions) delivered by the general practitioner (GP):				
	Session 1 (S1): Diagnosis, psycho-education, and "lifeline", in which the patients constructs a chronology of their most significant life events				
	Session 2 (S2): Narrative exposition, in which the patient recounts details of distressing situations that occurred in the Intensive Care Unit (ICU)				
	Session 3 (S3): Narrative exposition of a stressful event, extracted from the patient's lifeline ("PDS event")				
	Telephone calls (TC) $1-7$ : 7 telephone calls initiated by the GP practice affiliated medical assistant (MA) (S2, S3), including checking upon patients' well-being (PTSD-symptoms) and feedback to the GP.				
	Control intervention:				
	Improved treatment-as-usual (iTAU). GPs in the control group were instructed in evidence-based diagnosis and treatment of PTSD according to the S3-guideline. GPs contacted their patients for general checks and medical advice within 3 consultations (visit at GP's office).				
Trial Population	Adult male and female post-ICU patients aged 18 to 85 years (both inclusive), showing symptoms of PTSD.				

Trial Design	Prospective, national, multi-center, two-arm parallel-group (NET vs. iTAU), assessor-blinded, randomized controlled superiority trial with a psychological complex intervention delivered in the primary care setting					
Trial Objectives	Primary objective:					
	To demonstrate that the experimental intervention (NET) delivered by the GP is effective in reducing post-traumatic stress symptoms after intensive care measured by the PDS-5 total severity score, as compared to improved treatment as usual (iTAU)					
	Secondary objectives:					
	To demonstrate that NET is effective compared to iTAU in improving					
	a) symptoms of depression and anxiety					
	b) health-related quality of life, disability, and patient activation measure					
	To demonstrate a favorable cost-effectiveness of NET compared to iTAU ("PICTURE-Economics")					
	To describe the experiences of GP's in learning and implementing a psychotherapeutic treatment method in practice and how patients perceive the offer and the performance of a psychotherapeutic treatment delivered by their family physician ("PICTURE-Psychotherapy" add-on project)					
	To check for the occurrence of adverse effects of the intervention					
Trial Endpoints	Primary Efficacy Endpoint:					
	• Posttraumatic Stress (Posttraumatic Diagnostic Scale for DSM-5): absolute change in PDS-5 total severity score from baseline to T1 (6 months after baseline)					
	Secondary Endpoints:					
	• Posttraumatic Stress: absolute change in PDS-5 total severity score from baseline to T2 (12 month after baseline)					
	• Depression (PHQ-9 total score): absolute change from baseline to T1 and T2					
	• Anxiety (OASIS total score): absolute change from baseline to T1 and T2					
	• EQ-5D-5L: VAS at T1 and T2					
	• Disability (WHODAS 2.0 total score): absolute change from baseline to T1 and T2					

	Patient Activation Measure (PAM-13 total score): absolute change from baseline to T1 and T2					
	• "PICTURE-Economics":					
	Cost-effectiveness at T1 and T2 – based on direct/ indirect costs as measured via modified CSSRI (Client Sociodemographic and Service Receipt Inventory) applied and QALYs (EQ-5D-5L index values)					
	"PICTURE-Psychotherapy"  Qualitative aspects of attitudes and care of PTSD-patients in primary care					
Subject Numbers	To be assessed for eligibility:	N = 3000 patients (GPs) in total				
	To be allocated to the trial:	N = 340 patients (GPs) in total will be randomized (i.e. 170 per treatment arm)				
	To be analyzed:	N = 318 patients (GPs) in total (Recruitment concluded Dec 31 st , 2022)				
Trial Specific	Patient questionnaires (includ	ling mode of administration)				
Measurements	• PDS-5 (Posttraumatic Stress): self-complete version on paper (by default at T0, T1, T2); or (telephone-) interview version (for non-responders at T0, T1, T2)					
	PHQ-9 (Depression)					
	OASIS (Anxiety)					
	• EQ-5D-5L visual analogue scale (VAS); descriptive system: validated self-complete version on paper at T0, validated telephone interview version at T1, T2					
	Disability (WHODAS 2.0, 12-item version)					
	PAM-13 (Patient Activate)	vation Measure)				
	
 
modified version of CSSRI: interview version (assessed by the GP at T0; telephone interview version at T1 and T2)
 
					
Statistical Rationale	Primary efficacy analysis:					
	The primary efficacy endpoint is the absolute change in PDS total severity score ( $\Delta_6$ PDS) from baseline (T0) at month 6 (T1), no matter if derived from the PDS-5 questionnaire administered by mail or phone at T1.					
	The combined null hypothesis for the primary efficacy endpoint at T1 is that distributions of absolute change score values are the same for NET and iTAU in patients with and without missing scores. Under the					

alternative hypothesis, we expect a shift in distributions with a clinically relevant standardized effect size in the order of 0.36 (Cohen's d). To test the null hypothesis of the confirmatory principal analysis, we will use a two-sample t-test assuming a normal distribution of the  $\Delta_6 PDS$  variable. The principal analysis will be performed according to the intention-to-treat (ITT) principle, unadjusted for baseline covariates or site. The significance level is set to alpha = 5% (two-sided). The confirmatory principal analysis will be verified using multivariate models adjusting for sociodemographic factors, drop-out and potential confounders.

#### Secondary endpoints and secondary analyses:

All secondary analyses will be exploratory, i.e. without adjustment for multiplicity, using adequate descriptive statistics as well as bivariate and multivariate statistical methods. The corresponding 95% confidence intervals for treatment group effects will be reported.

#### Safety analysis:

Safety analyses will be performed in the safety population. All observed safety events will be summarized using standard descriptive statistics stratified by the NET vs. iTAU conditions.

#### Health economic evaluation ("PICTURE-Economics"):

On the basis of the EQ-5D-5L index values and data reported by means of the modified CSSRI questionnaire, cost-effectiveness will be described by the incremental cost-effectiveness ratio (ICER), i.e. the ratio between the cost and effect differences between intervention and control group. To assess the uncertainty associated with the ICER, a series of net-benefit regressions will be performed, and a cost-effectiveness acceptability curve will be constructed.

## Process evaluation ("PICTURE-Psychotherapy")

To investigate the subjective perception of the narrative intervention for patients and GPs respectively, as well as the perception of GP's in terms of delivering and usability of the NET-oriented therapy and the perception of patients in terms of relevance and impact, semi-structured interviews were conducted in a small subset of NET-participants with patients and GPs for qualitative analysis.

# 2 Schedule of Activities and Assessments

	STUDY PERIOD						
	Screening period		Enrolment and allocation		Post-allocation		
TIMELINE	T -1 Screening	2 weeks prior to T0 Re-Screening	Т 0	Randomi- zation (≤2 weeks after T0)	Intervention period (3 visits)	T 1 (6 month after T0)	T2 (12 month after T0)
Patient Informed Consent	X*		Х				
Eligibility Screen	Х	Х					
Patient level: In-/Exclusion Criteria			х				
PC-PTSD-5	Х	Х					
SIS	Х						
GP level: In-/Exclusion Criteria; GP characteristics		х					
GP Informed Consent		Х					
ICU Data (incl. SOFA score)	х						
Patient medical history, demographics/ characteristics	х		х				
Covid-19 Burden Scale (started 03/20)			х			х	х
Experimental intervention (NET)				« –	<del>></del>		
Control intervention (iTAU)				< −	>		
Documentation of SAE**				< −			>
PDS-5			Х			Х	Х
PHQ-9			Х			Х	х
OASIS			Х			Х	Х
EQ-5D-5L			Х			Х	Х
PAM			Х			Х	Х
WHODAS 2.0			Х			Х	Х
Modified CSSRI (incl. concomitant (drug) therapy, sociodemographic data)			х			х	х
Documentation of concomitant medication / therapy			х				
Check of compliance, protocol adherence (patient and GP level)			х		х	Х	х

\*Patient Informed Consent for Screening; \*\* Safety documentation: to be performed by the treating GP starting at S1 (NET-condition). A deviation from the schedule of +/-3 weeks is acceptable for T1 and T2.

[figure not shown]

Figure 1: Graphical depiction of study activities and components of intervention

### 3 Trial Objectives and Endpoints

The overall goal of the PICTURE trial is to evaluate whether a primary care based NET-oriented intervention improves patient-reported outcomes such as PDS total severity score, quality of life, common co-morbidities depression and anxiety in patients with PTSD after ICU discharge. This study aims to describe and compare the real-world effectiveness safety and applicability of a primary care based complex psychological intervention with improved "usual care".

#### 3.1 Add-on projects

Three sub-studies will be conducted together with the PICTURE – PTSD after ICU Survival-trial ("PICTURE-Economics", and "PICTURE-Psychotherapy in general practice").

#### 3.2 Primary Objective

The primary objective of the trial is to determine the effect of the NET-oriented therapy compared to iTAU, on patient-reported PTSD symptoms measured by the PDS total severity score after 6 month.

#### Primary study hypothesis:

The NET-oriented intervention is more effective than iTAU in improvingPTSD symptoms measured via the PDS total severity score.

#### 3.3 Primary Endpoint

The primary efficacy endpoint is defined as the absolute change in PDS-5 total severity score from baseline to T1, i.e. the difference between the 6-month post-randomization score and baseline score assessed at T0.

#### 3.4 Secondary Objectives

*The secondary objectives of this trial are:* 

- a) To assess the effects of the NET-oriented intervention compared to iTAU with respect to
  - depression symptoms
  - anxiety symptoms

Hypothesis: Depression is a comorbid disorder commonly associated with PTSD (Campbell et al., 2007) and observed post ICU (Davydow, Gifford, Desai, Bienvenu, & Needham, 2009). Anxiety disorders are common prevalent comorbidities following posttraumatic symptoms (Zlotnick et al.,

2006). NET effects were demonstrated in reduction of severity/diagnosis, depression, suicidality, anxiety and drug abuse (Schauer, Neuner, & Elbert, 2011).

- b) To assess the effects of the NET-oriented intervention compared to iTAU with respect to
  - health-related quality of life
  - Disability
  - Patient Activation Measure
- c) Objective of the health economic evaluation ("PICTURE-Economics")

To determine whether the NET intervention is cost-effective from a societal perspective compared to iTAU in patients diagnosed with PTSD after ICU survival.

We hypothesize that the NET-treated patients will cause lower health care costs and lower productivity losses compared to patients assigned to the iTAU condition while gaining a larger number of quality-adjusted life years, according to a better quality of life.

d) To check for the occurrence of adverse effects of the intervention

#### 3.5 Secondary Endpoints

- PDS-5 total severity score: absolute change from baseline at T2
- PHQ-9 total score: absolute change from baseline to T1 and T2
- OASIS-D total score: absolute change from baseline to T1 and T2
- EQ-5D-5L: VAS at T1 and T2
- WHODAS 2.0 total score: absolute change from baseline to T1 and T2
- PAM total score: absolute change from baseline to T1 and T2

#### 3.6 Additional secondary endpoints for "PICTURE-Economics"

Costs (CSSRI)

at T1 and T2.

- QALYs (calculated using the EQ-5D-5L index values)
- incremental cost-effectiveness ratio

SAP Version 1.4 July 2023

#### 3.7 Safety Variables

The occurrence of safety events (SAE) between S1 in the NET-group/the first of three GP-consultations in the iTAU-group and T2, e.g. death, major depression or suicidality, hospitalization, and referral for psychiatric care, will be assessed systematically by the GP during the consultations. Any indications of SAE will be documented and reported to the PI and the data safety and management board (DSMB) (See section 13).

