6.6 Safety Variables

The occurrence of safety events (SAE) between T0 and T2, e.g. death, major depression or suicidality, hospitalization, and referral for psychiatric care, will be assessed systematically by the GP during the consultations. Any indications of SAE will be documented and reported to the PI and the data safety and management board (DSMB) (See section 13).

7 Trial Design

7.1 General design issues:

This investigator-initiated study is designed as a prospective, randomized, multi-center, two-arm parallel-group, assessor-blinded, controlled, comparative effectiveness trial with a fixed sample design and a pragmatic attitude.

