12.3 Experimental group

GP Training:

After randomization, GPs in the intervention group will additionally receive a NET manual, a NET video and will be trained (3h) in delivering the NET-oriented intervention (in groups of 3-6 GPs) delivered by locally based and trained master psychologists or MDs within 4 weeks after baseline visit. The training video shall provide information on the theoretical background and practical application of the NET-therapy. If group training is not possible, training will be delivered on a one-to-one basis.

MA Training:

MAs will receive the NET-oriented intervention manual and a teaching video within 4 weeks of baseline.

Session 1 (45 min):

Within the framework of the PICTURE-study, the patient visits her/his GP within 6-10 weeks after T0. During session 1 (S1) psycho-education and recall of relevant life events ("drawing of a lifeline") will take place. During psychoeducation the patient will be informed about the symptoms usually associated with PTSD. The treatment procedures are described to the patient.

Together with the GP, the patient will construct his "lifeline". This symbolizes the patient's main events of his life along a rope that serves as a timeline. The GP gets an overview of stressful events in the patient's biography, as well as positive experiences that may serve as resources.

At the end of session 1, the patient is introduced to a MA, who will assist her/him throughout the study period. A photo of the lifeline is to be taken for monitoring purposes.

Additionally, the following session will be planned and the two PDS events to be discussed in S2 and S3 will be identified. PDS events are traumatic experiences in the patients' life, which may have left unpleasant memories. If these memories have lost association with the contextual and episodic memory system, these patients might develop PTSD.

The ICU experience being the event to be discussed during session 2 and another major life event to be discussed in session 3.

Session 2 (45 min):

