12.6.4 Treatment period

NET-group

The treatment period will include 3 visits (“sessions”) over a period of 6 weeks 6 to 10 weeks after T0.

- S1: Part 1 of intervention, to be scheduled 6 weeks (+/-4 weeks) after T 0
- S2: Part 2 of intervention, to be scheduled 2 weeks after S 1
- S3: Part 3 of intervention, to be scheduled 4 weeks after S 2

The following procedures will be performed regularly with about 2 week’s interval:

- 7 short TCs (without documentation of any study data) to be scheduled every 2-3 weeks after S2 to support NET sessions: 2 calls between S2 and S3, and 5 calls between S3 and T1.

The last TC will be performed 3 weeks before telephone interview T1

iTAU-group

There will be three GP consultations between T0 after randomization and T1 to be scheduled as required by the patient and are based on recommended standards (the S3-guideline; for example referral to psychiatric treatment, medication (e.g. anti-depressive), and general information about symptoms associated with PTSD). The consultations should be performed as a face-to-face appointment.

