12.6.5 Follow-up period

The structured telephone interview “T1” for the primary comparison will be scheduled 6 months (+/-3 weeks) after T0.

The final evaluation will be performed during a structured telephone interview “T2” to be scheduled 12 months (+/-3 weeks) after T0. This will be defined as the regular end of trial on the patient-level. For patients who terminate the trial prematurely (treatment discontinuation), but without withdrawing her/his consent, this will be defined as the “dropout telephone interview”.

13 Safety Data Collection, Recording and Reporting

For this trial, the rules of safety data collection, recording, and reporting as known from pharmaceutical trials do not apply. Hence, we make no distinction between adverse and severe adverse events. All events are hereafter referred to as severe adverse events (SAE).

Serious adverse events (SAE) will be regularly monitored and investigated as of beginning of the intervention at S1 in the NET-group and the first of three GP-consultations in the iTAU-group until the end of trial at T2. The GP is the first point-of-contact during the intervention period and telephone interviewers at T1 and T2. If a patient cannot be reached via telephone at T1 and T2, the RCT will contact the respective GP for further information with regard to the patient's possible SAE-status. Any SAE will be reported to the Principal Investigator (PI) and the Data and Safety Monitoring Board (DSMB). The respective SAE-Form (see appendix) will be faxed by the GP or RTC immediately (within 24 hours the latest) to the PI. In addition to the reporting of the event to the PI and the DSMB, any SAE recorded during telephone interviews at T1 and T2 will immediately be entered into the study database via OpenClinica.

SAE include psychiatric emergency treatment, psychiatric inpatient treatment/hospitalization, significant deterioration of depression or PTSD-symptoms, acute suicidality and suicide.

In case of SAE, psychiatric back-up specialist of the following institutions are available to provide immediate support through the Depts. of Psychiatry affiliated to the ITC in Munich and to the RTCs in Berlin, Dresden, Hamburg and Tübingen (letter of declaration). These emergency back-up centers will be instructed accordingly.

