13.5 Documentation and Reporting of Serious Adverse Events

Any SAE has to be reported immediately to the PI.

Documentation and evaluation of each SAE occurring:

- after the subject has been randomized and has received intervention
- up to the end of trial at T2

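### The SAE table starts at first contact with the assigned intervention, with no table from randomisation, no follow-up time and no defined safety population: a minor gap that is cheap to close

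*SAP*

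**What the plan says.** The start of SAE counting appears in several places, not all in agreement.

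- SAP 3.7 counts SAEs "between S1 in the NET-group/the first of three GP-consultations in the iTAU-group and T2". Death and hospitalisation are among its examples.
- Protocol section 13 monitors SAEs from the "beginning of the intervention at S1 in the NET-group and the first of three GP-consultations in the iTAU-group". Protocol 13.5 covers events occurring "after the subject has been randomized and has received intervention".
- Protocol 6.6, the counterpart of SAP 3.7, has "The occurrence of safety events (SAE) between T0 and T2" with no distinction by arm. The protocol synopsis and protocol 14.2 also name T0 to T2, but for the GP's safety documentation and monitoring, not for the count.
- The footnote to the schedule in SAP section 2 gives a start for NET only. SAP 8.1.4 refers to SAEs reported over the trial period.

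The two starting events follow different scheduling rules. In protocol 12.6.4, session 1 (S1) is "to be scheduled 6 weeks (+/-4 weeks) after T 0", and the protocol synopsis agrees. Protocol 12.3 says "the patient visits her/his GP within 6-10 weeks after T0", and the opening line of 12.6.4 also gives 6 to 10 weeks. For the control arm, 12.6.4 says "There will be three GP consultations between T0 after randomization and T1 to be scheduled as required by the patient", with no target week. Randomisation comes at most 2 weeks after T0 (protocol 9.1).

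SAP 8.1.4 reports, by arm, the number and percentage of patients with each SAE and of occurrences, with a descriptive look at the relation to treatment. It plans no test and promises a discussion of underreporting. The SAP synopsis places this analysis in a safety population. SAP 8.4 and protocol 15.4 define only the ITT and per-protocol populations.

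**The concern.** Checking for adverse effects of the intervention is a stated objective (SAP 3.4 d). The SAE window opens at an event that happens after randomisation, on a schedule that differs by arm. Three things follow if SAP 3.7 is applied as written.

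1. Events between randomisation and first contact are not counted. A patient who dies in that interval stays in the ITT population, and the null hypothesis in SAP 8.1.2 refers to times of death, yet the death would not appear in the SAE table.
2. A randomised patient who never reaches S1 or a first consultation has no counting window. The undefined safety population leaves open whether that patient is in the denominator.
3. The window can be longer in either arm. With percentages alone, a reader cannot separate a difference in SAE frequency from a difference in window length.

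**Working it through.** The documents give no SAE rate, safety sample size or date of first iTAU contact, so there is no figure of the plan's own to reproduce. The calculation below is an illustration.

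**Inputs from the documents.** 318 randomised at 1:1 (SAP 4.1 and 6), taken as 318/2 = 159 per arm. T2 at 12 months, taken as week 52, with a tolerance of 3 weeks either way. S1 at week 6, with week 10 as the upper limit in every statement of its timing. Randomisation no later than week 2.

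**Assumptions.** First iTAU consultation on average at weeks 2 to 14. Constant SAE hazard, equal in both arms. Risk of at least one SAE over 50 weeks of 20%, with a range of 10% to 40%.

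**Window ratio, NET/iTAU** = (52 − S1 week) / (52 − first iTAU week).

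- S1 at week 6: 46/50 = 0.92 (iTAU week 2) to 46/38 = 1.21 (iTAU week 14).
- S1 at week 10: 42/50 = 0.84 to 42/38 = 1.11.
- T2 tolerance, S1 at week 6: with T2 at week 49, 43/47 = 0.915 and 43/35 = 1.229; with T2 at week 55, 49/53 = 0.925 and 49/41 = 1.195. The tolerance matters little.

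**Patients with an SAE in a window of w weeks** = 159 × (1 − (1 − p)^(w/50)).

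At p = 0.20 this gives 31.8 for 50 weeks, 29.5 for 46, 27.2 for 42 and 24.8 for 38. The NET minus iTAU difference arising from window length alone is:

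| S1 week | p | iTAU start week 2 | iTAU start week 14 |
|---|---|---|---|
| 6 | 0.10 | −1.2 | +2.5 |
| 6 | 0.20 | −2.3 | +4.7 |
| 6 | 0.40 | −4.0 | +8.5 |
| 10 | 0.20 | −4.6 | +2.4 |

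**For scale**, the sampling SD of the difference in counts is √(2 × 159 × p × (1 − p)), which is 7.1 at p = 0.20.

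**Uncounted period in NET.** With randomisation at week 2 and S1 at week 6 to 10, 4 to 8 of 50 weeks (8% to 16%) fall before counting starts. By the same formula, about 2.8 to 5.6 of 159 patients would have an event in that period at p = 0.20. Over p = 0.10 to 0.40 the range is 1.3 to 12.5.

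**The case against.** The best defence is that the plan has already chosen. SAP 3.7 follows the protocol's dedicated safety section and replaces T0 with first contact. The principle is the same in both arms: count from the first contact of the assigned intervention. For an objective about adverse effects of the intervention, that is a sound convention. The table is also descriptive and untested, and underreporting will be discussed. Every size given here depends on an assumed SAE risk and assumed iTAU start times.

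All of this stands, and it is why the point is minor. It does not supply a denominator, does not place never-starters, and does not show events between randomisation and first contact.

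A second objection concerns the remedy. Protocol 12.5 mentions the time and duration of sessions and consultations, but for iTAU it then names only the number of consultations. First-consultation dates may therefore not always be held, and it cannot be confirmed that SAE onset dates are. Person-time also does not correct for closer contact in NET, where the SAP synopsis describes seven assistant calls with feedback to the GP. These limits stand and are carried into the fix.

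**Conclusion.** A minor gap that is cheap to close. Counting from first contact is acceptable, but it should not be the only SAE table, and the safety population needs a definition. In the main scenario (S1 at week 6, iTAU start at weeks 2 to 14, 20% risk, 159 per arm, constant equal hazard), window length alone moves the NET count by about 2 fewer to 5 more patients, against a sampling SD of about 7. The direction is unknown, because the documents do not give actual start dates or the number of never-starters. The primary analysis is not touched.

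Three stronger readings are not supported.

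- A reader might infer that SAEs in never-starters are lost. Protocol section 13 also records SAEs at the T1 and T2 interviews, and adds: "If a patient cannot be reached via telephone at T1 and T2, the RCT will contact the respective GP for further information". What is missing is a statement of whether those events count.
- A reader might infer that the rule favours NET. The window ratio lies on either side of 1 within the assumed range.
- A reader might infer that the SAP simply departs from the protocol. The conflict is inside the protocol, and the SAP agrees with its sections 13 and 13.5.

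**What to change.** In SAP 8.1.4, keep the table from first contact and add:

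- a table of SAEs from randomisation to T2 in all randomised patients, as randomised, using SAEs already recorded, including deaths and events found at the T1/T2 interviews or through GP contact;
- by arm, the number who never reached a first session or consultation and, where the dates are held, follow-up time and events per person-time.

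In SAP 8.4, define the safety population and say how never-starters are handled. Reconcile the SAE start across SAP 3.7, the SAP section 2 footnote and SAP 8.1.4, and protocol 6.6, 13, 13.5 and 14.2. Reconcile the timing of S1 across the protocol synopsis, 12.3 and 12.6.4.

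The cost is SAP wording, one table and a few summaries, with no new visits or GP enquiries. The report should state the limits. Events before first contact may be incompletely captured and partly recalled at T1 or T2. Some first iTAU consultation dates and SAE onset dates may be missing. Person-time does not remove the difference in contact frequency between arms. The second table therefore stands beside the first and does not replace it.
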